6.7.3 NCI-IRB Reporting of IND Safety Reports

Only IND Safety Reports that require a sponsor recommended change to meet the protocol or the consent form or in the opinion definition of the PI increases risks to study participants an unanticipated problem will need to be reported to the NCI IRB.

7 PHARMACEUTICAL INFORMATION

7.1 [F-18]-5-Fluoro-2'-deoxycytidine (FdCyd) NSC# 755309

7.1.1 Molecular Formula:

7.1.2 Molecular Weight:

244.2

7.1.3 How Supplied:

5-fluoro-2'-deoxycytidine is supplied as a sterile, single use vial. [F-18]-5-Fluoro-2'-deoxycytidine (FdCyd) Injection is formulated in sterile saline and is manufactured by the University of Pennsylvania, Philadelphia, PA. It is prepared for each patient on the day of administration and shipped to the address below:

Division of Radiation Safety
National Institutes of Health
[name]
[name]
[name]

The dose is 5 mCi or less at the time of administration, a mass dose of <30mg

7.1.4 Storage:

Intact vials should be stored at controlled room temperature. An expiration time will be listed on vial label

7.1.5 Route of Administration:

Intravenous

7.1.6 Preparation:

The agent is manufactured according to the University of Pennsylvania Standard Operating Procedures.

7.1.7 Method of Administration:

FdCyd may be mixed tetrahydrouridine (THU NSC 112907) in D5W and is stable for at least 24 hours at room temperature. See Section 5.4.2 for details about [F-18]-FdCyd administration.

Abbreviated Title: [F-18] FdCyd Imaging
Version Date: 03-09-2015
Protocol Number: CTEP 8865, NCI 12-C-0014

7.1.8 Availability

[F-18]-5-Fluoro-2'-deoxycytidine (FdCyd) Injection is an investigational agent supplied to investigators by the University of Pennsylvania.

7.1.9 Agent Ordering

NCI-supplied agents may be requested by the Principal Investigator (or their authorized designee) at each participating institution

¹⁸F FdCyd will be ordered directly from the University of Pennsylvania.

7.1.10 Agent Accountability

Agent Inventory Records – The investigator, or a responsible party designated by the investigator, must maintain a careful record of the inventory and disposition of all agents received from DCTD using the NCI Drug Accountability Record Form (DARF). (See the CTEP home page at <http://ctep.cancer.gov> for the Procedures for Drug Accountability and Storage and to obtain a copy of the DARF and Clinical Drug Request form.)

7.2 Tethydrouridine (THU) (NSC 112907)

7.2.1 Tethydrouridine (THU) Injection

Chemical Name: 2(1H)-pyrimidinone, tetrahydro-4-hydroxy-1.β.-D-ribofuranosyl-

Other Names: THU, H₄U

CAS Registry Number: 18771-50-1

Molecular Formula: C₉H₁₆N₂O₆ **M.W.:** 248

Approximate Solubility: The drug is highly soluble in water up to 200 mg/mL at pH 7.0.

Mode of Action: Cytidine deaminase inhibitor

How Supplied: Tethydrouridine Injection is supplied by the DCTD and distributed by the PMB/NCI as a 500 mg vial (10 mg/mL; 50 mL). The clear, colorless solution contains 10 mg tethydrouridine per mL with dibasic phosphate, USP, monobasic phosphate, USP used as buffer to maintain pH at 7.4.

Preparation: Tethydrouridine may be administered without further dilution or may be further diluted in 0.9% Sodium Chloride Injection, USP or 5% dextrose injection, USP to a concentration as low as 2.5 mg/mL.

Storage: Intact vials should be stored in the refrigerator (2° – 8°C).

Stability: Shelf life stability testing of the intact vials is on-going. Tethydrouridine as diluted above is stable for at least 24 hours at room temperature.

CAUTION: The single-use vial contains no antibacterial preservatives. Therefore, it is advised that the product be discarded 8 hours after initial entry.

Route of Administration: Intravenous for subjects enrolled from NCI Protocol 09-C-0214 (CTEP# 8351)

Abbreviated Title: [F-18] FdCyd Imaging

Version Date: 03-09-2015

Protocol Number: CTEP 8865, NCI 12-C-0014

7.2.2 Tetrahydrouridine Powder for Oral Solution (NSC 112907)

Chemical Name: 2(1H)-pyrimidinone, tetrahydro-4-hydroxy-1.β.-D-ribofuranosyl-

Other Names: THU, H₄U

CAS Registry Number: 18771-50-1

Molecular Formula: C₉H₁₆N₂O₆ **M.W.:** 248

Approximate Solubility: The drug is highly soluble in water, up to 200 mg/mL.

Mode of Action: Cytidine deaminase inhibitor

How Supplied: Tetrahydrouridine is supplied by the DCTD and distributed by the PMB/NCI in a single-use amber plastic bottle, with a tamper-evident cellophane seal around the bottle neck, containing 3 grams of Tetrahydrouridine Powder for Oral Solution.

Preparation for Oral Administration: Reconstitute each 3 gram bottle with 30 mL water (distilled or tap water may be used). Swirl to dissolve powder.

Storage: Store intact bottles and reconstituted solution in the refrigerator (2-8°C).

Stability: Shelf life stability testing of the intact bottles is on-going. Reconstituted solutions are stable in the amber plastic bottle for up to 3 weeks at refrigerated temperature.

Route of Administration: Oral for subjects enrolled from NCI Protocol 12-C-0066 (CTEP# 9127)

Method of Administration: THU oral solution should be taken on an empty stomach at least 1 hour before or 2 hours after a meal, and 30 minutes before FdCyd dosing. Immediately prior to dosing, patients should mix the reconstituted THU oral solution with 2-3 ounces of an acidic juice to aid in masking the taste (i.e., orange juice, apple juice or lemonade).

7.2.3 Agent Ordering

NCI-supplied agents may be requested by the Principal Investigator (or their authorized designee) at each participating institution. Pharmaceutical Management Branch (PMB) policy requires that agent be shipped directly to the institution where the patient is to be treated. PMB does not permit the transfer of agents between institutions (unless prior approval from PMB is obtained). The CTEP-assigned protocol number must be used for ordering all CTEP-supplied investigational agents. The responsible investigator at each participating institution must be registered with CTEP, DCTD through an annual submission of FDA Form 1572 (Statement of Investigator), Curriculum Vitae, Supplemental Investigator Data Form (IDF), and Financial Disclosure Form (FDF). If there are several participating investigators at one institution, CTEP-supplied investigational agents for the study should be ordered under the name of one lead investigator at that institution.

Active CTEP-registered investigators and investigator-designated shipping designees and ordering designees can submit agent requests through the PMB Online Agent Order Processing (OAOP) application (<https://eapps-ctep.nci.nih.gov/OAOP/pages/login.jsp>). Access to OAOP requires the establishment of a CTEP Identity and Access Management (IAM) account (<https://eapps-ctep.nci.nih.gov/iam/>) and the maintenance of an “active” account status and a “current” password. For questions about drug orders, transfers, returns, or accountability, call

Abbreviated Title: [F-18] FdCyd Imaging

Version Date: 03-09-2015

Protocol Number: CTEP 8865, NCI 12-C-0014

[contact] Monday through Friday between 8:30 am and 4:30 pm (ET) or email [contact] anytime.

7.2.4 Agent Accountability

The Principal Investigator or a responsible party designate by the PI will retain a careful record of the inventory and disposition of all agents received from DCTD using the NCI Drug Accountability Record Form per CTEP Policy and Guidelines for Accountability and Storage of Investigational Drugs (http://ctep.cancer.gov/protocolDevelopment/default.htm#agents_drugs).

8 STUDY CALENDAR

Patients on the IV FdCyd + THU protocol (NCI Protocol# 09-C-0214: CTEP#8351) will receive THU at least 20 minutes prior to and through the imaging. On their on-therapy scan (repeat imaging session), they will additionally receive cold FdCyd as prescribed by the referring protocol.

Patients on the oral FdCyd + THU protocol (NCI Protocol 12-C-0066: CTEP#9127) will receive THU approximately 2 hrs (+30 minutes) prior to the imaging. On their on-therapy scan (repeat imaging session), the patients will receive their therapeutic FdCyd + THU approximately 2 hrs (+30 minutes) prior to the imaging.

PET/CT Imaging Sessions					
	Baseline Evaluation	Day of imaging	0h	+2.0h	+1 day
¹⁸ F-5-Fluoro-2'-Deoxycytidine ^A (¹⁸ FdCyd)			X		
Informed consent	X				
Demographics	X				
Medical history	X				
Physical exam	X				
Record Concurrent Meds	X	X	X		
Performance status	X				
β HCG or urine pregnancy test		X			
Adverse Event evaluation	X	X	X		X
Vital Signs	X				
3 Dynamic regional Serial whole body PET/CT Imaging ^B			X		
Static Repeat whole body PET/CT Imaging				X	

^A: CTEP IND Agent: ~5mCi ¹⁸F-5-Fluoro-2'-Deoxycytidine single intravenous injection

^B: PET/CT imaging sessions will be performed pre-cycle under the Phase II FdCyd + THU protocol (NCI Protocol # 09-C-0214: CTEP# 8351 or Phase I FdCyd + THU protocol (NCI # 12-C-0066: CTEP 9127) and while receiving FdCyd + THU as prescribed by the protocol (2-5 days after cycle initiation)

9 MEASUREMENT OF EFFECT: IMAGE ANALYSIS

9.1 Tumor evaluation

- The location of the target lesion will be identified on the transmission CT

Abbreviated Title: [F-18] FdCyd Imaging

Version Date: 03-09-2015

Protocol Number: CTEP 8865, NCI 12-C-0014

- ^{18}F FdCyd uptake greater than or equal to 20% of the surrounding background (tumor to background ratio ≥ 1.2) will be considered to be qualitatively “positive”
- All regions/volumes of interest will be saved. Region volumes, and SUV values will be output to an Excel spreadsheet using MIM imaging software (www.mimsoftware.com)
- For lesions with uptake greater than background, an estimated smoothed maximum SUV (SUV_{max}) will be reported as the mean SUV value of an automated 80% maximum pixel value threshold based volume of interest (i.e. the average SUV of the “hottest” 20% of pixels in the user defined lesion). This method reduces the chances of the SUV_{max} value being dominated by one or more “noisy” pixel values.
- Volumetric ROIs will also be constructed based on manual tumor edge detection on transmission CT and a 50% SUV based threshold and the MIM Vista “PET edge” tool. These volumes will be used to estimate the total tumor tracer uptake and average uptake/gram of tissue.

A small VOI will be defined within the left ventricular cavity (LV), left atrium (LA) or largest vessel in the field of view. This will be used to obtain an image-derived input function.

Graphical analyses will be performed using the organ/tumor TAC and the image derived input function and

- Decay corrected time activity curves will be generated.

Analysis of the uptake will be dependent on whether a “reversible” or “irreversible” tracer uptake pattern is found. In addition to SUV values at discrete time points, either Logan or Patlak graphical analysis will be performed (corrected for metabolites if necessary), using an image based input functions. Kinetic analysis may also be performed if indicated.

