3 PATIENT SELECTION

3.1 Eligibility Criteria

3.1.1 Inclusion Criteria

- 3.1.1.1 Enrolled in the NIH Phase II Clinical protocol evaluating FdCyd with THU (NCI protocol # 09-C-0214 (CTEP# 8351) or NCI protocol #12-C-0066 (CTEP# 9127)) with target lesion measured as ≥ 10 mm with spiral CT scan.
- 3.1.1.2 Written, voluntary, informed consent of the patient must be obtained in compliance with institutional, state and federal guidelines
- 3.1.1.3 For females: Negative serum pregnancy test OR post-menopausal for at least 2 years OR patient has had a hysterectomy

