10 DATA REPORTING / REGULATORY CONSIDERATIONS

10.1 Data Collection

Data will be collected by the Molecular Imaging Program research nurse in a password-protected file in NCI C3D. The data will be entered at least on a weekly basis.

Data collection will include demographics, the site and size of the primary tumor, diagnosis date, biopsy date, and pathological diagnosis including tumor grade. Pharmacokinetic data will be generated and stored in a secure database. Raw image data will be stored on a secure external drive. Reconstructed imaging data will include storage of anonymized images from each time point and other extracted image parameters. This will be stored in a secure, password protected imaging database. Dosimetry (relative organ count rates and per cent injected dose estimates to the major organs) results will be calculated using OLINDA (Vanderbilt University, Nashville, Tennessee).

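### Section 9.1 reads tumour uptake straight off the image in lesions as small as 10 mm, so small-lesion uptake is expected to be biased low against normal organs, by an amount set by lesion size

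*Combined protocol and SAP*

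**What the plan says.** Section 3.1.1 (item 3.1.1.1) admits patients "with target lesion measured as ≥ 10 mm with spiral CT scan". Section 9.1 then applies one rule to every lesion: uptake with "tumor to background ratio ≥ 1.2" is labelled positive.

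Section 9.1 lists several ways of measuring tumour uptake:
- A smoothed SUVmax, taken as the mean inside "an automated 80% maximum pixel value threshold based volume of interest". The section also describes this as the average of the hottest 20% of pixels. The two descriptions do not coincide in general.
- Whole-lesion volumes: "Volumetric ROIs will also be constructed based on manual tumor edge detection on transmission CT and a 50% SUV based threshold", together with a PET edge tool. Their purpose is stated: "These volumes will be used to estimate the total tumor tracer uptake and average uptake/gram of tissue".

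It does not say which measure is the numerator of the 1.2 ratio. The only corrections it names are for decay and, if needed, for metabolites.

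For normal tissue, Section 9.2.1 places solid-organ regions inside a homogeneous part of the organ. Section 9.2.2 allows a spill-over adjustment, but only for hollow organs and only for dosimetry. No provision for lesion size or scanner resolution appears anywhere in the documents.

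**The concern.** PET blurs the image, so part of the signal of a small hot object spreads outside its borders and its measured contrast falls. A 10 mm lesion is only 1.25 to 2 times a resolution of 8 to 5 mm, so the loss is large. A region well inside the liver or muscle hardly loses anything.

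Secondary objective 1.1.2.2 concerns the distribution of FdCyd in tumorous and non-tumorous tissue, and Section 2.3 hopes that uptake will help explain why only a minority of patients benefit. If small-lesion values are attenuated and organ values are not, the comparison leans towards low tumour uptake. Differences in lesion size between patients, or between the two arms, can then look like differences in drug uptake. A cut-off only 20% above background is also easy to miss after a modest loss of contrast.

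**Working it through.** The plan states no recovery figure, resolution or sample-size argument for tumour uptake, so there is no figure of its own to reproduce.

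**Inputs from the documents:** smallest lesion 10 mm (Section 3.1.1); cut-off 1.2 (Section 9.1); the uptake measures of Section 9.1.

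**Assumptions:** uniform spherical lesion in a uniform background; Gaussian resolution of 5, 6, 7 or 8 mm FWHM; no noise and no motion; normal-organ regions for objective 1.1.2.2 drawn as in Section 9.2.1.

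**Step 1. Recovery.** A sphere on a 0.5 mm grid was blurred with a 3-D Gaussian. The recovery coefficient is RC = measured contrast / true contrast.

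| Diameter | RC, CT-volume mean (5 / 6 / 7 / 8 mm FWHM) | RC, hottest 20% (5 / 6 / 7 / 8 mm FWHM) |
|---|---|---|
| 10 mm | 0.52 / 0.44 / 0.37 / 0.31 | 0.74 / 0.61 / 0.50 / 0.40 |
| 15 mm | 0.67 / 0.61 / 0.55 / 0.50 | 0.93 / 0.86 / 0.78 / 0.70 |
| 20 mm | 0.75 / 0.70 / 0.66 / 0.61 | 0.98 / 0.96 / 0.91 / 0.86 |
| 30 mm | 0.83 / 0.80 / 0.77 / 0.73 | 1.00 / 1.00 / 0.99 / 0.98 |

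For total uptake, the 50%-threshold volume of a 10 mm lesion captures 0.40 / 0.34 / 0.32 / 0.31 of the true total (lesion signal alone, zero background).

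**Step 2. Effect on the ratio.** Measured ratio = 1 + RC × (true ratio − 1). Setting this to 1.2 gives the true ratio needed to be called positive: 1 + 0.2/RC. For a 10 mm lesion:
- Hottest 20%: from 1 + 0.2/0.74 = 1.27 at 5 mm to 1 + 0.2/0.40 = 1.50 at 8 mm.
- CT-volume mean: from 1 + 0.2/0.52 = 1.38 at 5 mm to 1 + 0.2/0.31 = 1.65 at 8 mm (1.64 with unrounded RC).

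The call therefore changes only for true ratios between 1.2 and an upper limit of 1.27 to 1.65, set by measure and resolution. (A single peak pixel, which Section 9.1 does not report, would put that limit at 1.23 to 1.43.)

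**Step 3. Dependence on the unnamed measure.** Take a 10 mm lesion with true ratio 1.5 at 7 mm FWHM:
- CT-volume mean: 1 + 0.37 × 0.5 = 1.19, below the cut-off.
- Hottest 20%: 1 + 0.50 × 0.5 = 1.25, positive.
- 80%-of-maximum threshold taken literally: about 1.19. At this low contrast the whole sphere lies above 80% of the maximum, so the result equals the CT-volume mean.

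The same lesion changes label according to a choice that Section 9.1 leaves open.

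**The case against.** Much of the case on the other side stands.

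- **Truly positive lesions turned negative.** A reader might infer that the plan will report such lesions as negative. The documents do not support that. Section 9.1 defines positive operationally, from the image ratio, and defines no negative class. Section 11 contains no positive rate, and no decision rests on the label. The 1.19 reading also depends on the measure chosen.
- **Lesion size not captured.** A reader might infer this because Section 10.1 lists only "the site and size of the primary tumor". But Section 9.1 saves every region and outputs region volumes, including the CT-edge volumes. Section 10.1 stores the images and Section 10.2 submits them. The size of the imaged lesion can be recovered, so nothing is lost for good.
- **A size limit.** A fixed 20 mm split, with smaller lesions below 1.2 called indeterminate, is tempting but unsound. At 20 mm the hottest 20% recovers 0.86-0.98 and the CT-volume mean 0.61-0.75, so 20 mm is not a clean boundary for both measures. Small lesions could then be only positive or indeterminate, so the positive rate among classified small lesions would be 100% by construction. Real information would also be discarded: in this model a 10 mm lesion with true ratio 1.2 reads 1.06-1.15, so a reading below about 1.06 points to a true ratio below the cut-off under every assumption. With 18 evaluable patients, two strata would also be very small.
- **Worst case.** The 10 mm figures describe the smallest eligible lesion, and the documents give no distribution of lesion sizes. Noise in a hottest-pixel measure, or spill-in from a hot neighbour, can shrink or reverse the bias in a single lesion.

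What remains is that the plan sets attenuated small-lesion values beside nearly unattenuated organ values and never says how to read the difference.

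**Conclusion.** The point holds as a limitation of the descriptive secondary analysis. In the model, contrast is lost at every assumed resolution: a 10 mm lesion loses roughly half to two-thirds of it on the CT-volume mean and about a quarter to 60% on the hottest 20%. The hottest-20% loss has almost gone by 30 mm; the CT-volume mean still loses 17-27% there. Strongly avid small lesions keep their positive label, but their SUV, total uptake and uptake per gram are still understated.

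The size rests on the sphere model and on an assumed resolution, so these are plausible ranges and not estimates for this scanner. The change from baseline to the scan 2-5 days into therapy is less affected, because the size of a given lesion should hardly change over that interval. The change is worth making but is not critical.

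**What to change.** In Section 9.1:

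1. Name the uptake measure that enters the 1.2 ratio, and settle whether the smoothed SUVmax is the 80%-of-maximum region or the hottest 20% of pixels.
2. Report tumour uptake and the ratio beside, or plotted against, the CT diameter of each imaged target lesion. The CT-edge volume V already output gives an equivalent diameter, (6V/π)^(1/3).
3. Add, as a sensitivity analysis for the tumour versus normal-tissue comparison, a recovery-corrected ratio, 1 + (measured ratio − 1)/RC, and the matching SUV. RC should come from the scanner's resolution and the CT diameter. In the 7 mm example, a hottest-20% reading of 1.25 returns 1 + 0.25/0.50 = 1.50.
4. Keep the 1.2 rule, but state that a ratio below 1.2 in a small lesion does not by itself show absence of uptake.

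No size cut-off or indeterminate class is needed.

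The cost is a few sentences and a little more analysis of images already kept. The correction amplifies noise and assumes a uniform sphere, so it should stay a sensitivity analysis beside the uncorrected values.

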9.2 Dosimetry Estimates

9.2.1 Solid Organs and Tumors

Regions of interest will be drawn within a homogeneous region within the organ of interest (identified on transmission CT if necessary). Anon decay corrected time activity curve (TAC) will be obtained from the serial whole body images

9.2.2 Hollow Organs

Regions encompassing the entire organ (i.e. gall bladder, intestine, bladder) will be initially drawn on CT and transposed onto the PET images. The final VOI’s may be adjusted for “spillover” based on the PET images. Total activity within the VOIs will be computed for each organ at each time point.

Residence times will be calculated from the time activity curves and dosimetry estimates will be calculated using OLINDA software.

10 DATA REPORTING / REGULATORY CONSIDERATIONS

10.1 Data Collection

Data will be collected by the Molecular Imaging Program research nurse in a password-protected file in NCI C3D. The data will be entered at least on a weekly basis.

Data collection will include demographics, the site and size of the primary tumor, diagnosis date, biopsy date, and pathological diagnosis including tumor grade. Pharmacokinetic data will be generated and stored in a secure database. Raw image data will be stored on a secure external drive. Reconstructed imaging data will include storage of anonymized images from each time point and other extracted image parameters. This will be stored in a secure, password protected imaging database. Dosimetry (relative organ count rates and per cent injected dose estimates to the major organs) results will be calculated using OLINDA (Vanderbilt University, Nashville, Tennessee).

10.2 Data Monitoring

This study will be monitored by the Clinical Data Update System (CDUS) Version 3.0. Data will be entered electronically on C3D and appropriate reports generated for periodic review.

Clinical Data: The investigators will provide quarterly reports of clinical data on the C3D clinical trial software. Cumulative C3D will be submitted quarterly to CTEP by electronic means.

Reports are due January 31, April 30, July 31, and October 31.

Imaging Data: DICOM datasets (or digital datasets for non-DICOM studies) - of the PET, PET-CT and pertinent anatomic studies the patients undergo on the trial will be submitted quarterly to CTEP via the NCIA (NCI Imaging Archive). The electronic transfer of image datasets is due January 31, April 30, July 31, and October 31.

10.3 Sample Storage, Tracking and Disposition

Blood samples will be collected for screening and on-study clinical laboratory safety assessments. All blood samples will be processed and handled in accordance with standard laboratory procedures. All samples will be analyzed at the NCI Clinical Center laboratory.

11 STATISTICAL SECTION

The purpose of the study is to determine the safety of [F-18]-5-fluoro-2'-deoxycytidine (FdCyd) administered intravenously with administration of tetrahydrouridine (THU). As such, the sample size is targeted at 18 evaluable patients, which is adequate to assess the toxicity rate. With 18 evaluable patients, the width of the 80% expected confidence interval of 10% and 20% toxicity rate is 0.18 and 0.24, respectively.

To account for the possibility of a small number of inevaluable patients, the accrual ceiling is set at 20 patients.

Accruing approximately 1 patient/ month, this protocol is expected to be completed within 1.5 years.

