The radioactive dose is 5 mCi or less at the time of administration.

2.1.3 Toxicity:

The quantity of [F-18]-FdCyd required for imaging is a microdose, and no toxicity is expected to be observed from the radiopharmaceutical. However, patients will be observed particularly for the toxicities noted in the animal and therapeutic studies. Based on the results of animal studies (1), the toxicities of a therapeutic dose of FdCyd are expected to be similar to those produced by 5-FdU and 5-FU, including neutropenia, mucositis, diarrhea, nausea and vomiting. This drug should be considered to have potential carcinogenic and teratogenic effects based on the carcinogenicity/teratogenicity of related drugs and on the teratogenic effects of FdCyd that have been reported in mice, including vertebral malformations, supernumerary limbs, and limb malformations.

During a Phase 1 therapeutic trial, additional toxicities possibly related to the FdCyd/THU were noted at FdCyd doses of 40 mg/m²/day 5 days a week for 2 weeks and above. These toxicities included electrolyte imbalances not immediately corrected with supplementation, elevated liver function tests, and anemia. None of the toxicities to date have had unresolved sequelae.

2.1.4 Pre-clinical Biodistribution for [18F]-FdCyd:

Radiation dosimetry estimates were based on rodent studies performed by IBA (the manufacturer of this radiotracer) under an NCI contract and the results are included in Table 1, and sample images are included in [Figure 3](#). Briefly, the estimated ED for the doses proposed in this study (5 mCi FdCyd) and transmission CT for a total of 2 imaging sessions) is 3.52 rem and the organs receiving the highest doses are the urinary bladder, liver, and kidneys.

Table 1

Radiation Dosimetry and Effective Dose Calculation		
Material:	F-18 FdCyd	
Dose/study	5	mCi
Subject Age:	ADULT	DOSE/STUDY
Organ	rad/mCi	rads
Adrenals	0.019	0.0955
Brain	0.001	0.0065
Breasts	0.004	0.01945
Esophagus¹	0.004	0.02085
Gallbladder Wall	0.031	0.154
Lower Large Intestine	0.038	0.192

Radiation Dosimetry and Effective Dose Calculation		
Material:	F-18 FdCyd	
Dose/study	5	mCi
Subject Age:	ADULT	DOSE/STUDY
Organ	rad/mCi	rads
Small Intestine	0.020	0.0975
Stomach	0.009	0.0459
Upper Large Intestine	0.018	0.091
Colon ²	0.027	0.13443
Heart Wall	0.009	0.04625
Kidney	0.125	0.625
Liver	0.145	0.725
Lungs	0.020	0.1015
Muscle	0.016	0.079
Ovaries	0.036	0.182
Pancreas	0.016	0.081
Red Marrow ³	0.011	0.0555
Bone Surfaces ⁴	0.007	0.03645

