5.3 Stopping Rules

For the purpose of protecting patient safety, the study will be stopped according to the following stopping rule.

Table 2

Number of Patients	Number of Grade 3 or 4 CTCAE toxicity
3-6	3
7-12	4
13-18	5

The operating characteristic of the stopping rule was assessed by simulations. Based on 10,000 simulations, the probability of stopping early for an excess of grade 3 or 4 CTCAE toxicity over the course of trial is 4.6% when the toxicity rate is 0.10 and 84% when the toxicity rate is 0.35. This is deemed reasonable for protecting patient safety.

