12.3 Evaluation of Benefits and Risks/Discomforts

There is no possibility of direct benefit to participants in this Phase 0 study. The results of this trial could generate generalizable information that may benefit future patients with cancer and therefore, subjects may benefit by knowing they have contributed to scientific knowledge.

The risks for participating are also small. Non-radiolabeled FdCyd has been administered to patients at higher doses under the parent study, and at this lower chemical dose (< 5mg) no FdCyd related adverse events are expected. No adverse effects are expected from tetrahydrouridine infusion.

Specific risks and potential complications will be clearly outlined in a separate consent form at the time of each procedure. Most complications are expected to be minor and require no treatment. Risks and discomforts associated with [F-18]-FdCyd PET/CT imaging are discomfort of an IV placement and the theoretical effects of additional radiation exposure (ED estimated at 3.52 rem). The subject will be required to lay still on their back for ~60 minutes for the longest scan.

A licensed clinical practitioner will be immediately available during the injection and imaging period and they will be backed by the Clinical Center's Code team. If hospitalization is required the participant will be admitted. However, this is unlikely to occur based on what is known of these agents. There is an added inconvenience of having to return for a follow-up scan that the subjects will be made aware of.

Adverse events will be reviewed after every case and a decision will be made about moving forward to the next participant so that each participant will have the benefit of the prior participant's experience.

As this is a new imaging test, the alternative is to choose not to participate.

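### Do the 80% interval widths in section 11 need restating because the section 5.3 stopping rule can end the study before 18 patients?

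*Combined protocol and SAP*

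**What the plan says.** Section 11 states that "the sample size is targeted at 18 evaluable patients, which is adequate to assess the toxicity rate". The numerical support is the pair of widths: "With 18 evaluable patients, the width of the 80% expected confidence interval of 10% and 20% toxicity rate is 0.18 and 0.24, respectively". The only allowance for losing patients is that "To account for the possibility of a small number of inevaluable patients, the accrual ceiling is set at 20 patients". The section does not name an interval method, give the grade of toxicity it has in mind, or refer to the stopping rule.

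Under section 5.3, "the study will be stopped according to the following stopping rule". Table 2 sets the limits at 3 Grade 3 or 4 toxicities in 3-6 patients, 4 in 7-12 and 5 in 13-18. Section 5.3 reports that "the probability of stopping early for an excess of grade 3 or 4 CTCAE toxicity over the course of trial is 4.6" per cent at a rate of 0.10, and "84% when the toxicity rate is 0.35". It gives no figure for 20% and no schedule of looks. Section 12.3 bears on timing: "Adverse events will be reviewed after every case and a decision will be made about moving forward to the next participant". On the likely rate, section 2.1.3 says that "no toxicity is expected to be observed from the radiopharmaceutical".

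**The concern.** Safety is a primary objective, and the two widths are the only figures offered for 18 being enough. They are fixed-sample widths, yet the study has a sequential rule that can stop it sooner. At 20%, one of only two rates that section 11 uses, that could happen often, leaving fewer patients, a wider interval and an observed rate that is too high on average.

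The unnamed method adds to the worry. The widths agree with the simple Wald formula, and a Wald interval collapses to 0% to 0% when no toxicity is seen. With a tracer expected to cause none, 0 of 18 is a realistic result. For a first-in-human agent the upper limit is then the main safety statement, and it would be better not chosen after the data are in.

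**Working it through.** **Inputs.** From section 11: n = 18, 80% interval, rates 0.10 and 0.20, widths 0.18 and 0.24. From section 5.3: the Table 2 limits, 4.6% and 84%. Assumptions: two-sided interval (z = 1.2816), independent patients, at most one toxicity counted per patient, limits read as 'at least', and section 11's toxicity the same as Table 2's.

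**1. The stated widths.** Plug-in Wald width = 2 × z × √(p(1−p)/n).
- p = 0.10: 2 × 1.2816 × √(0.09/18) = 0.181.
- p = 0.20: 2 × 1.2816 × √(0.16/18) = 0.242.

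Both match. Mid-P intervals averaged over the binomial distribution at n = 18 give 0.182 and 0.236, which also round to 0.18 and 0.24. The widths therefore do not identify the method.

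**2. The stated stopping probabilities.** An exact recursion over patients and toxicities gives a total crossing probability of 4.64% at 0.10 and 83.5% at 0.35, against 4.6% and 84%. The totals are identical for looks after every patient, every three patients, or at 6, 12 and 18, so the published figures do not reveal which schedule was meant.

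**3. Stopping before patient 18 at a 20% rate.** With looks at 6, 12 and 18 this can be done by hand.
- Stop at 6: P(≥3 of 6) = 1 − 0.2621 − 0.3932 − 0.2458 = 0.0989.
- Stop at 12, from 0, 1 or 2 toxicities in the first six: 0.2621 × 0.0170 + 0.3932 × 0.0989 + 0.2458 × 0.3446 = 0.1280.
- Sum: 0.2269.

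Plug-in widths at n = 6, 12 and 18 are 1.0253/√n = 0.4186, 0.2960 and 0.2417. Their average is 0.0989 × 0.4186 + 0.1280 × 0.2960 + 0.7731 × 0.2417 = 0.266.

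The recursion gives all three schedules:

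| | Every patient | Every three | 6, 12, 18 |
|---|---|---|---|
| Stop before 18, rate 10% | 4.18% | 3.58% | 3.34% |
| Stop before 18, rate 20% | 30.12% | 25.15% | 22.69% |
| Mean n, rate 20% | 15.6 | 15.9 | 16.0 |
| Mean observed rate, true rate 20% | 24.2% | 23.4% | 22.9% |
| Average plug-in width, rate 10% | 0.185 | 0.184 | 0.184 |
| Average plug-in width, rate 20% | 0.274 | 0.269 | 0.266 |

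**4. What a stopped study shows.** The least extreme stops allowed by Table 2 are 3 of 6, 4 of 12 and 5 of 18. At a rate of 10% the binomial tails are P(≥3 of 6) = 0.016, P(≥4 of 12) = 0.026 and P(≥5 of 18) = 0.028. All are below 0.10, so after any stop an ordinary exact 80% interval lies wholly above 10%. With the repeated looks counted, the chance of any stop at 10% is the 4.6% already published.

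**5. Would naming an exact interval help?** Coverage of nominal 80% intervals at a true 20% rate under the rule (every patient / every three / 6, 12, 18) is 74.6 / 75.4 / 76.7% for Wald and 77.3 / 75.4 / 76.7% for Clopper-Pearson. The two are equal under two of the three schedules.

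**6. No events in 18.** P(0 of 18) = 0.95^18 = 0.40 at a 5% rate and 0.90^18 = 0.15 at 10%. The 80% intervals are 0 to 0 for Wald, 0 to 8.4% for Wilson, 0 to 8.6% for mid-P and 0 to 12.0% for Clopper-Pearson.

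**The case for a change.** The strongest case for a change is that 20% is the sponsor's own planning rate, that at this rate the condition of 18 patients fails in about a quarter of trials, and that three or four sentences would cure it at no cost in patients. Table 2 also states no attribution to the tracer, so Grade 3 or 4 events from the parent therapy could lift the counted rate above what the tracer alone would produce. Averaged over true rates of 15 to 30%, with review after every patient, coverage of nominal 80% intervals is 70% for Wald, 71% for Wilson and 74% for mid-P, against 85% for Clopper-Pearson.

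The arithmetic stands, and so does the observation that section 11 neither names a method nor refers to section 5.3. The inference to a needed change is weaker. The 15 to 30% range is not in the documents and leaves out the 10% planning rate, where Wald under the rule covers 80.4%. Part of the Wald shortfall is present at a fixed 18 as well (76% over the same range), so it is not all due to stopping. At 20% itself, Clopper-Pearson gains little or nothing. The 0% to 0% interval arises only if Wald is used, and step 1 shows that the plan's widths do not establish that.

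**Conclusion.** No change to the plan is needed. The widths 0.18 and 0.24 are right on the condition that the sentence itself states. The stopping rule makes almost no difference at 10%. At 20% it raises the average plug-in width from 0.24 to about 0.27 and the mean observed rate to about 23 to 24%. That loss falls in trials that have met the study's own criterion for excess toxicity, where the answer is already clear enough to act on. This is the ordinary price of a safety rule.

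The unnamed interval is a gap that an analyst fills sensibly: nobody reporting 0 of 18 would give 0% to 0%, and the choice between exact, mid-P and Wilson is a matter of preference here. Confirming the method, and noting in the report that the observed rate tends to run high if the rule stops the study, are optional courtesies.

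The sizes rest on section 11's toxicity being Table 2's Grade 3 or 4 toxicity, on one outcome per patient, and on a look schedule that section 5.3 does not state. Review after every case, as in section 12.3, points to the upper end of 23 to 30%.
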